Participants will access the study via an online link provided by email or via word of mouth. They will first answer a question to assess their suicide risk. If they have not had suicidal thoughts in the previous three weeks, they will continue on to the study. If they indicate they have had such thoughts in the prior three weeks, they will be disqualified from the study and a screen will appear with contact information regarding mental health resources. [name] will then reach out to Student Counseling Services and ask them to reach out to the students to follow-up and provide additional support. For those students who continue with the study, they will take the PHQ-9 and the GAD-7 to measure their depression and anxiety levels. If they score 5 or above on either test they will be invited to participate in the therapy part of the study. In this part of the study the participant will be assigned to either receive individual teletherapy or group teletherapy for 12 weeks. This therapy takes place via text. Participants may be asked to read psychoeducational materials and complete homework assignments. Participants assigned to the individual therapy, will receive support in the form of direct asynchronous communication with the therapist. Participants assigned to the group therapy will receive support in the form of direct asynchronous communication with the therapist and asynchronous communication with peers struggling with similar issues. Throughout the at week 4, 8 and 12 of therapy, participants will take the GAD-7, PHQ-9, and self-report questionnaires to measure their engagement and experience.

Describe the location where research activities will take place:

The research will take place on participants personal electronic devices by logging on to the web-based TheraGroup platform. TheraGroup is a proprietary real-time virtual based platform that provides text based group therapy. It is a cloud software that offers HIPAA compliant asynchronous text chat.

How long will the participants be engaged in research? (length of time, i.e. 15 minutes on day 1, etc.):

up to 12 weeks

During data collection, describe what steps will be taken to ensure participant privacy:

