The current mental health crisis across college campuses particularly impacts students at Historically Black Colleges and Universities (HBCUs), who, compared to their Predominantly White Institution (PWI) counterparts, have fewer resources and less funding to support student psychological health [1]. While online therapy offers benefits, it does not solve the issue that the number of available therapists is insufficient to treat the number of students seeking help [2]. A promising solution is to increase opportunities for group therapy, which is equivalent to individual therapy in terms of outcomes [3]. As such, the purpose of our study is to assess the impact of an online, group text based therapy (one mental health counselor to many students) against a one-to-one (one mental health counselor to one student) therapy among HBCU students. Specifically, we will compare a HIPPA compliant, guided group telehealth (GGT) therapy (group therapy) called TheraGroup against a HIPPA compliant individual telehealth (IT) therapy (individual therapy) on measures of engagement, user experience, and mental health outcomes. If outcome measures in the GGT group are in line with outcome measures in the IT group, the feasibility study will serve as a precursor to testing the effects

RISKS AND BENEFITS

Describe any potential risks or discomforts to the participant (including physical, psychological and/or social):

Risks to subjects are rated as "Low", "Medium", "High". Do not say "none".

participants may be at risk of psychological harm. As the survey measures and therapy intervention ask participants to explore their mental health, specifically difficulties they may be having and traumatic events they have previously experienced, this process may exacerbate pre-existing mental health

Describe any potential benefits to the research participant or society:

Participants in this study will benefit from receiving mental health treatment from qualified professionals. Identifying effective group telehealth therapies to increase the access to mental health interventions contributes not only to the expansion of scientific knowledge within the field of mental health, but also to practical applications. Based on the findings of this study, interventions, trainings, and supports can be developed to treat mental illness in Black college students. This has potential

Describe alternatives to participation/opportunity to withdraw:

Participants may withdraw at any time

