If Yes, attach debriefing form and briefly describe deception:

PROCEDURES

What will participants be asked to do? (Describe the study in detail from recruitment to completion)
If you need additional space, put "see attached" in the box below and attach complete description of procedures.

Participants will access the study via an online link provided by email or via word of mouth. Next, they will take the PHQ-9 and the GAD-7 to measure their depression and anxiety levels. If they score 5 or above on either test they will be invited to participate in the therapy part of the study. In this part of the study the participant will be assigned to either receive individual teletherapy or group teletherapy for 12 weeks. This therapy takes place via text. Participants may be asked to read psychoeducational materials and complete homework assignments. Participants assigned to the individual therapy, will receive support in the form of direct asynchronous communication with the therapist. Participants assigned to the group therapy will receive support in the form of direct asynchronous communication with the therapist and asynchronous communication with peers struggling with similar issues. Throughout the at week 4, 8 and 12 of therapy, participants will take the GAD-7, PHQ-9, and self-report questionnaires to measure their engagement and experience.

Describe the location where research activities will take place:

The research will take place on participants personal electronic devices by logging on to the web-based TheraGroup platform. TheraGroup is a proprietary real-time virtual based platform that provides text based group therapy. It is a cloud software that offers HIPAA compliant asynchronous text chat.

How long will the participants be engaged in research? (*length of time, i.e. 15 minutes on day 1, etc.*):

up to 12 weeks

During data collection, describe what steps will be taken to ensure participant privacy:

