7. Trouble concentrating on things, such as reading the newspaper or watching television
8. Moving or speaking so slowly that other people could have noticed. Or the opposite being so fidgety or restless that you have been moving around a lot more than usual
9. Thoughts that you would be better off dead, or of hurting yourself

GAD-7

Over the last two weeks, how often have you been bothered by the following problems?

Scale: 0 = not at all; 1 = several days; 2 = more than half the days; 3 = nearly every day

1. Feeling nervous, anxious, or on edge
2. Not being able to stop or control worrying
3. Worrying too much about different things
4. Trouble relaxing
5. Being so restless that it is hard to sit still
6. Becoming easily annoyed or irritable
7. Feeling afraid, as if something awful might happen

Engagement

On a scale from 1 to 5 with 1 being not at all to 5 being completely, rate how much the following statement applies to your experience with the telehealth therapy program:

1. I was interested in the therapy
2. I was intrigued when I used the telehealth therapy services
3. I was focused when I used the telehealth therapy services
4. I enjoyed using the telehealth therapy services

5. It was boring to use the telehealth therapy services
6. I felt frustrated using the telehealth therapy services
7. I found the telehealth services confusing
8. I felt unmotivated to use the telehealth services

User Feedback Experience

1. What, if anything, did you enjoy about your experience in using the guided telehealth therapy?
2. What, if anything, could be improved about your experience in using the guided telehealth therapy?
3. Did you feel the psychoeducational content was culturally relevant to you as a Black individual? Please explain

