Statistical Analysis Plan

Official Study Title: Guided group telehealth to deliver evidence-based therapeutic care to Black college students

NCT Number:

Date of Document: 03/10/2025

Statistical Analysis Plan

To test the primary hypothesis that participants in the Guided Group Telehealth (GGT) condition will experience reductions in depression and anxiety comparable to those in the Individual Telehealth (IT) condition, we will use a mixed-design repeated measures ANOVA. The within-subjects factor will be time (baseline, week 4, week 8, and week 12), and the between-subjects factor will be therapy condition (GGT vs. IT). The dependent variables will be PHQ-9 and GAD-7 scores, measuring depression and anxiety, respectively. Interaction effects will be examined to assess whether changes in symptom severity over time differ between the two conditions. For secondary analyses, we will use independent samples t-tests to compare user engagement and user experience scores between the two conditions at week 12. Descriptive statistics will be used to summarize engagement data, including participation rates, message frequency, and task completion. Additionally, qualitative analysis will be conducted on open-ended responses from the user experience survey to identify common themes related to participants' satisfaction and perceived effectiveness of the intervention. All analyses will be conducted using an alpha level of 0.05, and effect sizes will be reported alongside p-values. If violations of normality or sphericity are detected, appropriate corrections, such as Greenhouse-Geisser adjustments or nonparametric alternatives, will be applied.

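### Engagement is scored at weeks 4, 8 and 12, but the only planned arm comparison is a week-12 t-test that ignores the earlier scores of students who do not respond at week 12

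*SAP*

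**What the plan says.** The protocol's Procedures section states that "at week 4, 8 and 12 of therapy, participants will take the GAD-7, PHQ-9, and self-report questionnaires to measure their engagement and experience". The instrument, listed under Engagement in the survey measures, has eight items rated "On a scale from 1 to 5 with 1 being not at all to 5 being completely". The Purpose of Study section says the two therapies will be compared "on measures of engagement, user experience, and mental health outcomes".

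The SAP's secondary analysis is "independent samples t-tests to compare user engagement and user experience scores between the two conditions at week 12". Its repeated-measures model does not reach engagement: "The dependent variables will be PHQ-9 and GAD-7 scores, measuring depression and anxiety, respectively". The remaining engagement data are only described: "Descriptive statistics will be used to summarize engagement data, including participation rates, message frequency, and task completion".

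Neither document gives an analysis population, a missing-data method or an expected dropout rate. The protocol (Risks and Benefits) lets participants withdraw whenever they wish.

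**The concern.** Two of the three planned engagement assessments have no arm comparison attached to them. An independent-samples t-test at week 12 can use only students who answer at week 12. Someone who rated the service boring or frustrating at week 4 and then stopped responding is left out, although the score was recorded.

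Engagement is the first comparison named in the study purpose. If non-response follows engagement and one arm loses more students than the other, the week-12 responders in the two arms are selected to different degrees, and the difference between them no longer estimates the difference between the arms as assigned. When the less engaging arm also loses more students, a real gap is understated. When there is no gap, unequal selection can create one.

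**Working it through.** **Inputs from the documents.** Three post-baseline engagement assessments (Procedures), one of them tested (SAP), a maximum sample of 200 (Subject Recruitment) and alpha 0.05 (SAP). There is no effect size, SD, dropout rate or power statement for engagement, so there is no figure of the plan's own to reproduce.

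**Assumed inputs.** 100 per arm (no allocation ratio is stated), two-sided testing, correlation r = 0.6 between visits unless varied, and the dropout patterns below.

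**Step 1: selection, in SD units.** 2,000 simulated trials per setting. The chance of missing week 12 follows a logistic model on the mean of the week-4 and week-8 scores, with slope 0 (unrelated), 1 or 2. Differences are GGT minus IT among week-12 responders.

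| Lost by week 12 (GGT / IT) | Dropout related to engagement? | True gap 0: mean estimate | True gap 0: rejection rate | True gap -0.40: mean estimate | True gap -0.40: power |
|---|---|---|---|---|---|
| none | n/a | about 0 | about 0.05 | about -0.40 | about 0.81 |
| 30% / 30% | yes | about 0 | about 0.05 | about -0.40 | 0.66 to 0.72 |
| 40% / 20% | no | about 0 | 0.05 | -0.40 | 0.63 |
| 40% / 20% | yes | +0.10 to +0.15 | 0.08 to 0.15 | -0.30 to -0.25 | 0.44 to 0.34 |
| 50% / 20% | no | about 0 | 0.05 | -0.40 | 0.59 |
| 50% / 20% | yes | +0.15 to +0.22 | 0.13 to 0.25 | -0.25 to -0.18 | 0.28 to 0.19 |

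Bias needs both conditions: dropout related to engagement, and unequal retention. In the 50% / 20% case, the fall in power from 0.81 to 0.59 is loss of numbers. The further fall to between 0.28 and 0.19 is selection.

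**Step 2: one dropout rule for both arms.** Retention can become unequal simply because one arm is less engaged. Under a common rule, a true gap of 0.40 fell to about 0.37 to 0.30. With no true gap, a common rule produced no bias.

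**Step 3: a milder case, in scale points.** True gap 0.40 points, SD 0.8, r = 0.6, dropout on the last score, retention 68 to 80% in the better arm and 55 to 74% in the worse. The week-12 gap averaged 0.34 to 0.39, so the largest bias is 0.40 - 0.34 = 0.06 points. At the lowest retention the standard error is 0.8 × sqrt(1/68 + 1/55) = 0.145, so the bias is 0.06 / 0.145 = 0.41 of a standard error.

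**Step 4: what the earlier scores recover.** In Steps 2 and 3, and under unequal dropout rules, a likelihood estimate using all three visits averaged about 0.40. This is expected, because the simulated non-response depended only on recorded scores.

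**Step 5: precision.** With no dropout and equal correlations, the mean of three scores has (1 + 2r)/3 of the variance of one score.

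- r = 0.5: 2.0/3 = 0.67, worth 1/0.667 - 1 = 50% more participants.
- r = 0.6: 2.2/3 = 0.73, worth 36%.
- r = 0.7: 2.4/3 = 0.80, worth 25%.

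This applies only to the visit-averaged contrast with a constant gap. With complete data, a model with free arm-by-visit means gives the same week-12 difference as the t-test and gains nothing there. If the gap grows as 0.2, 0.3, 0.4, the averaged gap is 0.3, or 0.75 of the week-12 gap. At r = 0.6 its z-value is then 0.75 / sqrt(0.733) = 0.88 of the week-12 z-value, a loss.

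**The case against.** Week 12 is a legitimate prespecified time point. The items ask about experience with the programme and set no recall window, so an end-of-therapy answer can be read as a rating of the whole course, and one fixed visit avoids choosing among visits. This stands, and it is why week 12 should remain the main contrast. It does not justify ignoring the earlier scores of students who miss that visit.

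A reader might infer that the week-12 test includes only students engaged enough to remain, or that week 12 is the worst visit to use. The documents do not establish either. Surveys run through Qualtrics, separately from the platform logs, and nothing says whether students who stop therapy are still surveyed. Payments rise: $5, $50 and $100 are listed for Times 1 to 3, and the recruitment email's $305 maximum implies 305 - 155 = $150 for Time 4. That could keep disengaged students answering.

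A reader might also infer that the test always makes the arms look alike and so favours the study's hypothesis. The table shows otherwise: with no true gap, unequal engagement-related dropout produces a false difference. The SAP's hypothesis of comparability concerns depression and anxiety, not engagement.

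Finally, the log-based summaries may cover early leavers and would help reveal arm-specific disengagement, but no arm comparison is specified for them. The lack of a missing-data method also affects every outcome in the plan, and the attrition part of this point is one instance of it.

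**Conclusion.** The point holds in a limited form. It is certain from the text that engagement is measured three times, that the arms are tested once, and that students who do not answer at week 12 drop out of that test whatever they recorded earlier. Whether this biases the result depends on two things the documents do not tell us: whether non-response follows earlier engagement, and whether retention differs by arm. If both occur, the assumed scenarios range from a bias under half a standard error to a 0.40 SD gap being roughly halved. If either is absent, the week-12 estimate was unbiased in these simulations.

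The 25 to 50% sample-size equivalent should not be read as a free gain for the planned comparison, because it does not apply to the week-12 difference. The consequence is confined to a secondary analysis, and nothing here undermines the PHQ-9 and GAD-7 analysis.

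**What to change.** Replace the engagement t-test in the SAP with a mixed model for repeated measures on the week 4, 8 and 12 scores, with arm, visit and arm-by-visit terms and an unstructured covariance. Include every assigned student with at least one engagement score. Keep the week-12 arm difference as the main contrast, with a 95% confidence interval. Report the difference averaged over visits as supplementary, and report week-12 questionnaire completion by arm.

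The cost is a change of SAP wording, with no new data. There are three downsides to state. The model removes bias only if non-response is explained by observed scores, so non-response driven by unrecorded disengagement would bias it too. Its week-12 standard error can be slightly larger than the t-test's under heavy dropout. The averaged contrast answers a different question, and it loses power if the gap widens over time.
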